7.4 DOSE LIMITING TOXICITY

In reporting adverse events we will follow the final regulations issued by the Food and Drug Administration addressing the safety reporting requirements for investigational new drug applications (INDs) found in 21 CFR part 312 and for bioavailability and bioequivalence studies found in 21 CFR part 320. "Safety Reporting Requirements for INDs and BA/BE Studies".

<http://www.fda.gov/downloads/Drugs/GuidanceComplianceRegulatoryInformation/Guidances/UCM227351.pdf>

The classification for adverse events to be used is the following:

- 1 Mild adverse event; did not require treatment
- 2 Moderate adverse event; resolved with treatment
- 3 Severe adverse event; inability to carry on normal activities; required professional medical attention
- 4 Life-threatening or permanently disabling adverse event
- 5 Fatal adverse event

In this grading system, “**severe**” is not equivalent to *seriousness*.

The definitions to be employed will follow the final regulations issued by the FDA in September 2010 “Safety Reporting Requirements for INDs and BA/BE Studies”, and described in section 7.4 of this protocol.

Dose limiting toxicity (DLT) is defined as any adverse event that is possibly, probably, or definitely related to the study agent. This would include any grade 3 event according to the classification given above.

Study enrollment will be halted by the investigators when any subject experiences a Grade 3, or higher adverse event toxicity that is possibly, probably, or definitely related to the study drug.

Laboratory tests with values within the clinically significant range will be repeated during the same visit whenever possible (refer to Table 6.4 for a complete list of clinically significant range values). If the test result returns after the subject leaves the clinic, they will be immediately contacted. For local residents they will be asked to return to the outpatient clinic for a repeat test as clinically indicated. For non-local residents, arrangements will be made to have the blood test redrawn in a laboratory close to home or by their primary care physician. To avoid any confusion for the primary care physician, they will be informed (with permission from the subject) of their participation in the study at the time of gene transfer. If the AE requires treatment, this will be carried out by the primary care physician or a doctor of choice selected by the subject. We will obtain copies of repeat laboratory tests and any relevant medical records for addition to the subject’s research chart.

Only those adverse events requiring treatment will qualify as DLT. The PI will fulfill the reporting responsibilities under 21 CFR 312.32(c), to notify FDA in an IND safety report of potentially serious risks, as soon as possible, but no later than 15 calendar days after the investigator receives the safety information and determines that the information qualifies for reporting. The investigator will confer with the DSMB and FDA before continuing enrollment.

Table 6.4 Clinically Significant Laboratory Range

Test	Units	Reference Range		Clinically Significant Range
Hemoglobin	g/dL	2Y – 5Y	11.5 – 13.5	< 8.0 or > 18
		6Y – 11Y	11.5 – 15.5	
		12Y – Adult	12.0 – 16.0	
WBC	K/cu mm	4Y – 5Y	5.5 – 15.5	≤3.5 or ≥ 20
		6Y – 9Y	5.0 – 14.5	
		10Y – 20Y	4.5 – 13.5	
		21Y – Adult	4.5 – 11.0	
BUN	mg/dL	5 - 18		≥35
PT	sec	12.4 – 14.7		≤ 5.0 or ≥ 35.0
PTT	sec	24 - 36		≥ 125
Platelet	K/cu mm	140 - 440		≤ 90 or ≥ 800
Amylase	U/L	0 – 17Y	<110	≥ 200
		18Y – Adult	30 - 110	
Total Protein	g/dL	3Y – 15Y	5.8 – 8.7	≤4.4 or ≥ 9.5
		16Y – Adult	6.4 – 8.4	
Total Bilirubin	mg/dL	0.1 – 1.0 mg/dL		≥ 3.0
Creatinine	mg/dL	4Y – 7Y	0.3 – 0.8	≥ 1.8
		8Y – 10Y	0.3 – 0.9	
		11Y – 12Y	0.4 – 1.0	
		13Y – 17Y	0.5 – 1.2	
		18Y – Adult	0.6 – 1.3	
GGT*	U/L	8 – 78		3XULN

ULN= upper limit normal

* Subjects with history of alcohol abuse will be excluded from the study. Since GGT is very sensitive to alcohol consumption, subjects will be required to avoid alcohol the week before testing. For subjects taking drugs that potentially induce GGT synthesis through the cytochrome P450 system, the clinically significant range will be estimated at two times the levels obtained from the baseline screening test.

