7.5 STOPPING/DISCONTINUATION RULES

An independent Data Safety Monitoring Board (DSMB) will be established by the sponsoring agency including a safety monitor for the study. Safety data will be monitored on a continual basis throughout the trial. The DSMB can recommend early termination of the trial for reasons of safety. Study enrollment will be halted by the investigators when any subject experiences a Grade 3, or higher adverse event toxicity that is possibly, probably, or definitely related to the study drug. This will include:

- Grade 3
 - Severe or medically significant but not immediately life-threatening;
 - Hospitalization or prolongation of hospitalization indicated;
 - Disabling; limiting self care ADL**.
- Grade 4
 - Life-threatening consequences;
 - Urgent intervention indicated.
- Grade 5
 - Death related to AE.

Activities of Daily Living (ADL)

*Instrumental ADL refer to preparing meals, shopping for groceries or clothes, using the telephone, managing money, etc.

****Self care ADL refer to bathing, dressing and undressing, feeding self, using the toilet, taking medications, and not bedridden.**

If after review by the DSMB the decision is made to continue, the study will proceed according to Section 6.2.7.6 (Dose escalation) of this protocol.

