8.0 ADVERSE EVENT MONITORING AND REPORTING

8.1 DEFINITION OF AN ADVERSE EVENT

As stated above (6.2.7.4) this protocol will follow the final regulations issued by the Food and Drug Administration addressing the safety reporting requirements for investigational new drug applications (INDs) found in 21 CFR part 312 and for bioavailability and bioequivalence studies found in 21 CFR part 320. "Safety Reporting Requirements for INDs and BA/BE Studies".

<http://www.fda.gov/downloads/Drugs/GuidanceComplianceRegulatoryInformation/Guidances/UCM227351.pdf>

Adverse Events will be collected throughout the study from enrollment to last follow up visit.

Adverse Event (AE): Adverse event means any untoward medical occurrence associated with the use of a drug in humans, whether or not considered drug related.

Adverse events will be graded by the investigator accordingly:

Grade 1 Mild; asymptomatic or mild symptoms; clinical or diagnostic observations only; intervention not indicated.

Grade 2 Moderate; minimal, local or noninvasive intervention indicated; limiting age-appropriate instrumental ADL*.

Grade 3 Severe or medically significant but not immediately life-threatening; hospitalization or prolongation of hospitalization indicated; disabling; limiting self care ADL**.

Grade 4 Life-threatening consequences; urgent intervention indicated.

Grade 5 Death related to AE.

A Semi-colon indicates 'or' within the description of the grade.

A single dash (-) indicates a grade is not available.

Activities of Daily Living (ADL)

*Instrumental ADL refer to preparing meals, shopping for groceries or clothes, using the telephone, managing money, etc.

**Self care ADL refer to bathing, dressing and undressing, feeding self, using the toilet, taking medications, and not bedridden.

Association or relatedness to the study agent, study procedures and the subject's pre-existing disease will be graded as follows: 5 = unrelated, 4 = unlikely, 3 = possibly, 2 = probably, and 1 = definitely related.

Adverse reaction: An adverse reaction means any adverse event caused by a drug. Adverse reactions are a subset of all suspected adverse reactions for which there is reason to conclude that the drug caused the event.

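### Protocol section 7.4 gives two incompatible DLT rules, so related untreated events, including an untreated Grade 3 event, have no settled DLT status

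*Protocol*

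**What the plan says.** Protocol section 7.4 opens its DLT rule with "Dose limiting toxicity (DLT) is defined as any adverse event that is possibly, probably, or definitely related to the study agent" and continues "This would include any grade 3 event according to the classification given above". The first sentence sets no minimum grade and no treatment condition. The classification it refers to is the five-grade list in 7.4 itself, where Grade 1 is "1 Mild adverse event; did not require treatment" and Grade 2 is "2 Moderate adverse event; resolved with treatment" (the leading digits are the grades).

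After a paragraph on repeating out-of-range laboratory tests, the same section states "Only those adverse events requiring treatment will qualify as DLT". This sentence mentions neither relatedness nor grade. The rest of its paragraph covers safety reporting to FDA and then says that the investigator will consult the DSMB and FDA before enrolment goes on.

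Section 8.1 uses a different scale, repeated in SAP 6.6.2. Its Grade 2 reads "minimal, local or noninvasive intervention indicated; limiting age-appropriate instrumental ADL", and a note explains: "A Semi-colon indicates 'or' within the description of the grade". The halt rule in section 7.5 uses the 8.1 wording for Grade 3, beginning "Severe or medically significant but not immediately life-threatening". In the readable SAP text, DLT appears only in the abbreviation list.

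**The concern.** A DLT rule has to give one answer for each event. Here the answer depends on which sentence of 7.4 the reader applies, and nothing readable says which governs or that they apply together.

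The label is used in two places, and possibly a third:

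- Section 8.3 sends every SAE and every DLT to NIAMS and the DSMB within 48 hours.
- Section 12.1 puts SAE and DLT time points on each participant's timeline in the DSMB report, and the DSMB advises on escalation.
- Because the consultation requirement in 7.4 stands in the same paragraph as the treatment sentence, the label may also trigger it. On the widest DLT rule, a trivial related Grade 1 event would then require consultation before the next subject is dosed. Section 7.6 asks for consultation only on related events of Grade 3 or higher.

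**Working it through.** No arithmetic applies and the plan gives no figure to reproduce. The check applies each statement to each kind of related event.

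**Rules compared**

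- Rule A (7.4, definition plus Grade 3 sentence): related is enough, and Grade 3 on the 7.4 scale is named.
- Rule B (7.4, treatment sentence): an event that does not require treatment is not a DLT.
- Joint reading: related and requiring treatment.

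Section 8.1 says that an SAE is an event graded 3, 4 or 5 and restates the 8.1 grade text. The last column uses that rule.

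| Related event | Rule A | Rule B | Joint reading | 48-hour report as SAE by grade? |
|---|---|---|---|---|
| Grade 1, untreated | DLT | not DLT | not DLT | no |
| Grade 2, treated | DLT | not excluded | DLT | no |
| Grade 2 on 8.1 through limited instrumental ADL, untreated, not Grade 3 on 7.4 | DLT | not DLT | not DLT | no |
| Grade 3 on 7.4 but Grade 2 on 8.1, untreated | DLT, named | not DLT | not DLT, against the Grade 3 sentence | no |
| Grade 3 on both scales, untreated | DLT, named | not DLT | not DLT, against the Grade 3 sentence | yes |
| Grade 3 on both scales, treated | DLT | not excluded | DLT | yes |

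**What follows**

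1. The rules agree on treated related events and conflict on untreated ones.
2. On the 7.4 scale, the low-grade conflict is Grade 1, because Grade 2 there is treated by definition. On the 8.1 scale it can extend to Grade 2, since a semicolon means or, and limited instrumental ADL is enough without treatment.
3. The joint reading settles the low-grade rows but not the Grade 3 rows. An event that stopped normal activities and was seen by a professional, but needed no treatment, is Grade 3 on the 7.4 scale. The Grade 3 sentence includes it and the joint reading drops it.
4. An untreated event that is Grade 3 on the 8.1 scale reaches NIAMS and the DSMB within 48 hours as an SAE whatever its DLT status. The 48-hour report therefore depends on the label only for events below Grade 3 on 8.1. That includes the fourth row, where the two scales can disagree.

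**Rules that do not use the label**

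- The enrolment halt in 7.4, 7.5 and 12.1 is set by related Grade 3 or higher.
- The stopping criteria in 6.6 are set by one related Grade III or higher toxicity, or two or more related Grade II toxicities.
- Consultation under 7.6 is set by related Grade 3 or higher.

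**The case against.** The strongest reply is that the sentences are not contradictory: the later one narrows the earlier, so a DLT is a related event that requires treatment. That is a natural reading of a sentence beginning with the word only, and it would exclude the untreated low-grade events. It also fits the rest of the protocol better than Rule A, which could make every trivial related event a reason for consultation before enrolment continues. But the protocol does not state it. The sentence follows text on laboratory retests and may be meant for laboratory findings alone. The reading also still contradicts the express inclusion of any Grade 3 event. That case is narrow, because Grade 3 on the 7.4 scale involves professional medical attention, but attention need not mean treatment.

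It can also be said that the 8.1 scale should not be brought in, because the Grade 3 sentence points to the 7.4 list. That is right as to what the sentence names, and the conflict exists on the 7.4 scale alone. The 8.1 scale matters because 7.5 and SAP 6.6.2 grade events by it.

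Finally, the practical effect is small. This stands. Low-grade events still reach the DSMB, through data shared as gathered (6.7) and the AE listings (12.1). SAP 6.6.2 summarises treatment-related events and maximum grade by cohort.

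Three stronger readings are tempting, and the documents support none of them:

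- **The halt or stopping rules are compromised.** They are worded by grade and relatedness, not by DLT.
- **The MTD is undermined.** Protocol 2.0 and SAP 2.2 say an MTD will be established from toxicity, but no readable text ties it to a DLT count. Parts of 6.7 and 7.6 are blacked out, so a link can be neither shown nor ruled out.
- **Unrelated treated events become DLTs.** The treatment sentence is worded as a necessary condition, so it does not by itself make an event a DLT.

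**Conclusion.** Wrong as written, and minor. Section 7.4 states two DLT rules that cannot both be followed, and the most charitable combination still conflicts with the section's own Grade 3 sentence.

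The effect is limited to the 48-hour report for related untreated events below Grade 3 on the 8.1 scale, the DLT entries on the DSMB timeline, and possibly the consultation step in 7.4. The last depends on sentence placement: a sentence on FDA reporting stands between, so the requirement may attach to that instead.

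No numerical size can be given. The documents do not show how many events were related and untreated, and counting categories in a table would not measure it. The conclusion assumes that the blacked-out text holds no further DLT definition.

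**What to change.** Replace the DLT definition, its Grade 3 addition and the later treatment sentence with one rule: *a DLT is an AE whose relationship to the study agent is rated possible, probable or definite and which is Grade 3 or higher (on either the 7.4 or the 8.1 scale until one scale is adopted), or is of lower grade and requires treatment.* Use it in 7.4, 8.3 and the DSMB reports. Naming both scales matters: the 8.1 scale alone could drop an untreated event that is Grade 3 on 7.4 but Grade 2 on 8.1, which the present text includes.

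State also that consultation with the DSMB and FDA before enrolment continues applies to related events of Grade 3 or higher, as in 7.6.

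If the final report makes a DLT or MTD statement, base it on this definition and label the classification post hoc for subjects already dosed.

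The cost is a short text change. Compared with the joint reading, the rule adds only untreated related events of Grade 3 or higher. Those that are Grade 3 or higher on 8.1 are already 48-hour SAEs. Those that are Grade 3 only on 7.4 could add a 48-hour report, but the existing Grade 3 sentence already covers them. Compared with the literal definition, it removes untreated related events below Grade 3. Any DLT count means case-by-case review of related events in seven subjects. Past 48-hour reporting cannot be changed.

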7.5 STOPPING/DISCONTINUATION RULES

An independent Data Safety Monitoring Board (DSMB) will be established by the sponsoring agency including a safety monitor for the study. Safety data will be monitored on a continual basis throughout the trial. The DSMB can recommend early termination of the trial for reasons of safety. Study enrollment will be halted by the investigators when any subject experiences a Grade 3, or higher adverse event toxicity that is possibly, probably, or definitely related to the study drug. This will include:

- Grade 3
 - Severe or medically significant but not immediately life-threatening;
 - Hospitalization or prolongation of hospitalization indicated;
 - Disabling; limiting self care ADL**.
- Grade 4
 - Life-threatening consequences;
 - Urgent intervention indicated.
- Grade 5
 - Death related to AE.

Activities of Daily Living (ADL)

*Instrumental ADL refer to preparing meals, shopping for groceries or clothes, using the telephone, managing money, etc.

****Self care ADL refer to bathing, dressing and undressing, feeding self, using the toilet, taking medications, and not bedridden.**

If after review by the DSMB the decision is made to continue, the study will proceed according to Section 6.2.7.6 (Dose escalation) of this protocol.

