4.0 SPECIFIC AIMS

4.1 PRIMARY OBJECTIVE

Determine the safety of intravascular administration of self-complementary scAAVrh74.tMCK.hSGCA delivered via a major lower limb artery targeting all of the lower limb muscles of LGMD2D (alpha-SG deficient) subjects.

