6.6 OUTCOME MEASURES

The study is a Phase I/IIa clinical trial inclusive of safety and efficacy outcome measures

- A. Safety is the primary outcome for this clinical gene transfer trial. Stopping criteria are based on development of unacceptable toxicity defined as the occurrence of any one Grade III or higher treatment-related toxicities, or two or more Grade II treatment-related toxicities.

B. Efficacy outcome measures include:

i. Strength and functional testing will be performed at baseline and at days 60, 90, 180, and at 9, 12, 18, and 24 months. This will include the 6MWT distance as the primary functional variable. [REDACTED]

[REDACTED]

[REDACTED]

[REDACTED]

[REDACTED] Pre- and post-treatment strength, distance, and time will be evaluated by using paired t-tests.

[REDACTED]

[REDACTED]

[REDACTED]

[REDACTED]

[REDACTED]

[REDACTED]

[REDACTED]

[REDACTED]

[REDACTED]

[REDACTED]

[REDACTED]

[REDACTED]

iii. Immune response will be assessed by IFN- γ ELISpots to alpha-sarcoglycan and AAV capsid. A rise in IFN- γ of 50 spot forming colonies per one million PBMCs towards virus or transgene will be considered significant. An additional measure of immune response will be the binding antibody assay to AAV.

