7.6 DOSE ESCALATION

There will be 4 weeks between dosing of subjects within a cohort. For the first cohort, the allowance of four weeks between dosing of subjects provides time for safety review from five time points (days 1, 2, 7, 14 and 30) prior to dosing of the next subject and time for review of the safety analysis of all the subjects within a cohort by the investigators and the DSMB.

This timeline will also provide time for review of any clinically significant improvement based on the 6MWT data. [REDACTED]

[REDACTED]

The investigators will confer with the IRB, DSMB, and FDA/CBER on all grade – 3 or higher adverse events that are possibly, probably, or definitely related to the study agent before continuing enrollment. Based on the outcome of the safety and efficacy analysis at the end of each cohort decisions will be made to proceed with dose escalation for the following cohort.

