- A timeline outlining the study progress relative to visit number for each participant, as well as time points for each SAE/Dose Limiting Toxicity. A total for Adverse Events (AEs) for each participant should be included.
- A summary of AEs by severity levels;
- A listing of AE details grouped by participant;
- A listing of SAE details grouped by participant;
- A listing of deaths
- A summary of clinically significant laboratory test results
- A listing of protocol deviations

Stopping/Discontinuation Rules

An independent Data Safety Monitoring Board (DSMB) has been approved by the study's sponsor (National Institute of Health). Safety data will be monitored on a continual basis throughout the trial. The DSMB can recommend early termination of the trial for reasons of safety. Study enrollment will be halted and discussed with the DSMB by the investigators when any subject experiences a Grade 3 or higher adverse event toxicity that is possibly, probably, or definitely related to the study drug. This will include any subject death, important clinical laboratory finding, or any severe local complication in the injected area related to administration of the study agent. If after review by the DSMB, IRB, IBCSC, NIH-OBA and FDA,

the decision is made to continue, the study will proceed according to Dose Escalation plan.

MEMBERSHIP

The DSMB membership consists of persons completely independent of the investigator who have no financial, scientific, or other conflicts of interest with the trial. Current or past collaborators or associates of [REDACTED] must note any conflict of interest before their eligibility to serve on the DSMB is approved.

The DSMB will include experts in or representatives of the fields of:

- Neurology and Neuromuscular Diseases
- Immunology
- Gene Therapy
- Muscular Dystrophy Clinical Care
- Clinical Research and Clinical Trials

Conflict of Interest

Individuals invited to serve on the DSMB as either voting or non-voting members must disclose any potential conflicts of interest, whether real or perceived. Conflicts of interest can include professional, proprietary, and miscellaneous interests as described in the NIH Grant Policy Statement and 45 CFR Part 94. Potential conflicts that develop during a member's tenure on a DSMB must also be disclosed. Written documentation attesting to an absence of conflict of interest is required annually.

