6.6.2 Adverse Events

Adverse events (AEs) will be coded using the Medical Dictionary for Regulatory Activities (MedDRA) [Version 22.0].

AEs will be graded by the Investigator as follows:

- Grade 1: Mild; asymptomatic or mild symptoms; clinical or diagnostic observations only; intervention not indicated
- Grade 2: Moderate; minimal, local or noninvasive intervention indicated; limiting age-appropriate instrumental activities of daily living (ADL)*
- Grade 3: Severe or medically significant but not immediately life-threatening; hospitalization or prolongation of hospitalization indicated; disabling; limiting self-care ADL**
- Grade 4: Life-threatening consequences; urgent intervention indicated

Sponsor Protocol ID: 9004-101 Covance Study ID: 000000209191

Grade 5: Death related to AE

A Semi-colon indicates 'or' within the description of the grade.

- *Instrumental ADL refer to preparing meals, shopping for groceries or clothes, using the telephone, managing money, etc.
- **Self-care ADL refer to bathing, dressing and undressing, feeding self, using the toilet, taking medications, and not bedridden.

The relationship between an AE and study drug is assessed as definite, probable, possible, unlikely, or not related. A treatment-related AE is an AE considered by the investigator as definitely, possibly, or probably related to study drug or with unknown/missing relationship to study drug.

All AE data recorded in eCRF will be listed. In addition, a listing of serious AEs (SAEs) will be produced.

Treatment-emergent AEs (TEAEs) will be summarized by cohort and overall. TEAEs are AEs that occur or worsen in severity on or after gene transfer. AEs with missing start date will be considered as TEAEs.

TEAEs will be summarized by cohort and overall. An overview table will summarize the number and percentage of subjects with at least one of the following TEAEs, where subjects with more than one TEAE in a particular category are counted only once in that category:

- Any TEAE
- TEAE by maximum severity grade
- Treatment-related TEAE
- Any treatment-emergent SAE (TESAE)
- Treatment-related TESAE
- TESAE leading to death

The number of total TEAEs will be also included in the overview table.

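### The halt rule is inconsistent on severe vector-delivery injuries: 7.4, 7.5 and 7.6 require relatedness to the study drug or agent, while 12.1 arguably reaches further

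*Protocol*

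**What the plan says.** The primary objective (Protocol 4.1) covers the route as well as the vector: "Determine the safety of intravascular administration of self-complementary scAAVrh74.tMCK.hSGCA delivered via a major lower limb artery".

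The stopping language appears in five places.

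- **7.4:** "Study enrollment will be halted by the investigators when any subject experiences a Grade 3, or higher adverse event toxicity", if the event is at least possibly related to the study drug. Dose-limiting toxicity in the same section is also defined by relatedness to the agent.
- **7.5:** the trigger is a "Grade 3, or higher adverse event toxicity that is possibly, probably, or definitely related to the study drug". The list that follows only describes Grades 3, 4 and 5.
- **7.6:** the investigators confer with the IRB, DSMB and FDA on events of Grade 3 or above that are "possibly, probably, or definitely related to the study agent before continuing enrollment".
- **12.1:** the lead sentence has the same drug-relatedness condition. The next sentence says the trigger includes any subject's death, an important laboratory finding, or "any severe local complication in the injected area related to administration of the study agent".
- **6.6:** stopping follows "any one Grade III or higher treatment-related toxicities, or two or more Grade II treatment-related toxicities". The protocol does not define *treatment-related*.

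Section 8.1 asks for separate attributions: "Association or relatedness to the study agent, study procedures" and pre-existing disease are each graded from 5 (unrelated) to 1 (definite).

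**The concern.** An investigator can properly record an event as definitely related to the procedure and unrelated to the agent. The protocol foresees events of that kind. Section 11.3.2.2 lists permanent ischemic damage, compartment syndrome, and a hematoma that may need transfusion, surgery or a later discharge. Section 11.3.2.7 adds tissue damage from restricted blood supply. Prolonged hospitalization is itself a Grade 3 criterion in 7.5 and 8.1, so such events can reach the halting grade.

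Whether enrollment then stops depends on which section the investigator follows. In a trial whose primary question includes the safety of intravascular delivery, the next subject could be infused by the same technique before anyone has had to decide that this is acceptable.

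**Working it through.** **Step 1. Apply each rule to one case:** a Grade 3 limb-ischemia injury, definitely related to the procedure and unrelated to the agent.

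| Section | Relatedness test | Does enrollment halt? |
|---|---|---|
| 7.4 | Study drug | No |
| 7.5 | Study drug | No |
| 7.6 (duty to confer) | Study agent | Not required |
| 12.1, lead sentence | Study drug | No |
| 12.1, next sentence | Administration of the agent, injected area | Arguably yes |
| 6.6 | Treatment (undefined) | Unclear |

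**Step 2. Can 12.1 be settled from the text?** Two readings are open.

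- *Narrow:* the second sentence gives examples of drug-related events. In 7.5 the matching sentence only spells out the grades of such events.
- *Broad:* the sentence extends the rule. It names any subject's death without a relatedness test, and it refers to administration rather than the agent. Section 6.3 II places cannulation, heparinization and balloon occlusion inside vector administration.

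The broad reading is reasonable, but *injected area* is not defined for a whole-limb infusion, and 7.4 and 7.5 lack the sentence.

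**Step 3. Count the dosing steps exposed.** Cohort sizes are 1, 3 and 3 (synopsis).

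- All steps from one subject to the next: 7 − 1 = 6.
- Cohort boundaries (1A to 1B, 1B to 2): 2. Section 7.6 already requires a decision to proceed at each.
- Within cohort: (1 − 1) + (3 − 1) + (3 − 1) = 0 + 2 + 2 = 4. Check: 2 + 4 = 6.

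For the first cohort, 7.6 says that four-week spacing gives time to review safety from five time points before the next subject is dosed, with no relatedness filter. Section 7.3 lets intervals in the second cohort be shortened. I take first and second to mean low and high dose, as the 7.3 dose table numbers them; Cohort 1A has one subject and so no internal spacing. On that reading the 2 steps in Cohort 1B are softened and the 2 in Cohort 2 are the clearest gap. Section 7.3 elsewhere calls the high-dose group the third cohort, so this is an assumption. The total of 4 does not depend on it.

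**Step 4. Can the risk be quantified?** Only loosely. Section 11.3.2.2 gives upper bounds of 4% for a larger hematoma and 0.5% for a blocked or significantly damaged vessel. With independent events, the chance of at least one is 1 − (1 − p)^n, where n is 7 subjects or, if the risk applies per limb, 1 × 1 + 6 × 2 = 13 limbs.

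| Event | n = 7 | n = 13 |
|---|---|---|
| Hematoma, p = 0.04 | 24.9% | 41.2% |
| Vessel damage, p = 0.005 | 3.4% | 6.3% |

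These are ceilings for events of any grade and any attribution. The gap needs Grade 3 or above and a rating of unlikely or unrelated to the agent. The documents give no rate for that subset, nor any rate for ischemic injury.

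**The case against.** **The rule is not uniformly drug-only.** A reader might infer that 7.4, 7.5 and 12.1 all exclude delivery injuries. The documents do not support that, because the second sentence of 12.1 can naturally be read to cover a severe femoral-access or infused-limb injury. This stands, and it makes the point an inconsistency rather than a uniform omission.

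**The SAP does not narrow 6.6.** It is also tempting to read 6.6 as drug-only because the SAP (6.6.2) says "A treatment-related AE is an AE considered by the investigator as definitely, possibly, or probably related to study drug". That definition serves the adverse-event tables, goes on to include unknown or missing relationships, and stands in a document dated 25 April 2022 that was written from the protocol of 10 February 2017. It cannot show what the protocol's stopping criterion meant. The term in 6.6 is simply undefined.

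**Other safeguards exist.** Grade 3 to 5 events count as serious (8.1). All serious events go to the DSMB within 48 hours regardless of relatedness (8.3). Data are shared with the DSMB as gathered (6.7), and the DSMB can recommend termination (7.5). Section 7.6 provides review time in the first cohort. So it would be wrong to infer that such an event goes unreviewed. These safeguards are reporting, discretion and time, however; none makes the next infusion wait for a decision. Redacted lines follow the review text in 7.6, so a further gate there cannot be ruled out.

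**The class is narrow and the choice defensible.** *Possibly related* is a low bar for an agent just held in the injured limb, so some delivery injuries would halt enrollment anyway. Escalation seeks a maximum tolerated dose from toxicity, which favors an agent-based trigger. Both points lower the priority. Neither explains why 12.1 differs from 7.4 and 7.5.

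**Conclusion.** The concern holds as an inconsistency in a safety rule. For a Grade 3 or higher delivery injury rated unlikely or unrelated to the agent, 7.4 and 7.5 do not halt enrollment and 7.6 does not require conferring, while 12.1 arguably requires a halt.

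The exposure is at most 4 of 6 dosing steps: clearest at 2 (Cohort 2) and softened at 2 (Cohort 1B). This counts the schedule and does not measure risk. It rests on the cohort reading in the working and on the visible text of 7.6. Fewer steps may remain for an amendment to cover, since 11.3.2.11 reports events in subjects already treated and 11.6.3 planned enrollment to finish in December 2017.

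Priority is low to moderate. Confidence is medium, because the broad reading of 12.1 may be what was meant.

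**What to change.** State one rule in 7.5, and bring 7.4, 7.6 and 12.1 into line by cross-reference:

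> Enrollment stops, pending the reviews in 7.6 and 12.1, after any adverse event of Grade 3 or above whose Section 8.1 relatedness grade is 3, 2 or 1 either for the study agent or for the vector administration procedure in Section 6.3 II, including anesthesia, contrast, cannulation, heparinization, balloon or tourniquet occlusion, infusion and dwell.

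Keep the items named in 12.1 as triggers. Anesthesia and contrast belong in the list because 11.3.2.1 and 11.3.2.3 name life-threatening outcomes for them. Prednisone and blood draws are not added.

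The cost is a wording amendment. Relatedness to study procedures is already graded under 8.1; the investigator would also record whether the procedure was vector administration. Sample size and analyses do not change. The downside is an occasional enrollment pause for an event that says nothing about the vector.
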